7.1.7. Withdrawal Due to an Adverse Event

Any patient who experiences an adverse event may be withdrawn from the study or from study treatment at any time at the discretion of the investigator. If a patient is withdrawn wholly or in part because of an adverse event, both the adverse events page and termination page of the CRF will be completed at that time.

In addition, a blood sample will be aimed to be obtained, to the extent possible, for the measurement of study drug concentrations. The patient will be monitored at the discretion of the investigator (eg, until the event has resolved or stabilized, until the patient is referred to the care of a health care professional, or until a determination of a cause unrelated to the study drug or study procedure is made). The investigator must inform the Medical Monitor as soon as possible of all patients who are being considered for withdrawal due to adverse events. Additional reports must be provided when requested.

If a patient is withdrawn from the study for multiple reasons that include adverse events, the termination page of the CRF should indicate that the withdrawal was related to an adverse event. An exception to this requirement will be the occurrence of an adverse event that in the opinion of the investigator is not severe enough to warrant discontinuation but that requires the use of a

prohibited medication, thereby requiring discontinuation of the patient. In such a case, the reason for discontinuation would be need to take a prohibited medication, not the adverse event.

All patients for whom an adverse event of suicidal behavior/ideation was reported at any time during the study should be discontinued from study medication and the need for an evaluation by a psychiatrist should be assessed. Discontinued patients should attend an early termination visit to return study medication, perform drug accountability, and will be asked to complete all protocol required study procedures. Adverse events of suicidal behavior/ideation should be followed until resolution of the suicidal behavior/ideation.

All patients who are discontinued from the study medication due to active suicidal behavior/ideation should be referred to a psychiatrist and followed by the investigator until resolution of the suicidal behavior/ideation.

Patients who discontinue study medication due to safety or tolerability reasons may continue in the study off drug and perform the scheduled visits and assessments.

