5.3. Prior and Concomitant Therapy or Medication

Any prior or concomitant therapy, medication, or procedure a patient has had within 2 weeks prior to screening and up to the end of the study period will be recorded on the CRF. Generic or

trade name, indication, and dosage will be recorded. The sponsor will encode all therapy and medication according to the World Health Organization (WHO) drug dictionary (WHO Drug).

Medications that are not prohibited during the study (see Section 5.3.1) are allowed at the discretion of the investigator and will be documented in the CRF. To the extent possible, patients should continue on medications already prescribed at enrollment; dose modifications and introduction of new medications should be avoided unless deemed necessary for optimal patient care by the investigator.

Disallowed CYP2D6 substrates can be administered only 1 week after the discontinuation of pridopidine (i.e., 1-week washout), to allow enzyme recovery. CYP2D6 inhibitors can be administered to study patients. The concomitant use of medications that are known to have a profound effect on QT interval should be avoided according to the list of permitted and prohibited concomitant medications. [REDACTED]

[REDACTED] concomitant treatment with tetrabenazine is disallowed. Medications that are CYP2D6 substrates and have the potential to reduce the seizure threshold will not be permitted during the study.

Any changes to an existing concomitant medication or any new medication started during the study should be recorded in the CRF. For any concomitant therapy given as a treatment for a new condition or a worsening of an existing condition, the condition must be documented on the AE Form of the CRF.

If a patient receives a prohibited treatment during the randomized phase of the study, he/she will be encouraged to continue in the study and complete the study visits in accordance with the study visit schedule; however, the patient may need to be withdrawn from study treatment (see Section 4.4). If the patient refuses to be seen for further visits, the assessments for End-of-Study (EoS)/Early Termination should be performed, as far as possible (at least attempts to capture information on AEs and concomitant medication).

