7.1. Adverse Events

7.1.1. Definition of an Adverse Event

An adverse event is any untoward medical occurrence in a patient administered a pharmaceutical product, regardless of whether it has a causal relationship with this treatment.

In this study, any adverse event occurring after the clinical study patient has signed the informed consent form should be recorded and reported as an adverse event.

An adverse event can, therefore, be any unfavorable and unintended physical sign, symptom, or laboratory parameter that develops or worsens in severity during the course of this study, or significant worsening of the disease under study or of any concurrent disease, whether or not considered related to the study drug. A new condition or the worsening of a pre-existing condition will be considered an adverse event. Stable chronic conditions (such as arthritis) that are present before study entry and do not worsen during this study will not be considered adverse events.

New symptoms of HD or deterioration of previously existing symptoms should be recorded as an AE only if the presentation and/or outcome is more severe than would normally be expected from the normal course of the disease in a particular patient.

In any event of suspected suicidality or clinical findings suggesting that the patient is dangerous to him or herself at the moment of evaluation or during the duration of the clinical study, the patient should be discontinued from treatment with study drug, referred for **immediate** psychiatric evaluation and an AE/SAE should be reported. Patients with an AE/SAE of suicide ideation or attempt will be discontinued from treatment with study drug. Patients who are discontinued from treatment may continue their participation in the study and perform the scheduled visits and assessments, while off study drug.

Accordingly, an adverse event can include any of the following:

- intercurrent illnesses
- physical injuries
- events possibly related to concomitant medication
- significant worsening (change in nature, severity, or frequency) of the disease under study or other pre-existing conditions (Note: A condition recorded as pre-existing that is intermittently symptomatic [eg, headache] and that occurs during this study should be recorded as an adverse event.)
- drug interactions

- events occurring during diagnostic procedures or during any washout phase of this study

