7.1.6. Protocol-Defined Adverse Events for Expedited Reporting

Adverse events of suicidal ideations or attempt should be reported to the sponsor within 24 hours of learning of the event. The corresponding dedicated CRF should be completed, but the events should not be marked as serious unless deemed serious by the investigator. The words "protocol defined adverse event" should be added after the adverse event term. Once the adverse event of suicidal ideation or attempt is received, the patient should be discontinued from the study and from study medication, and referred to a psychiatrist for evaluation and monitoring (see Section 7.1.7).

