7.8. Other Safety Measures and Variables

7.8.1. Columbia Suicide Severity Rating Scale

The C-SSRS will be used to rate the patient's degree of suicidal ideation on a scale ranging from "no suicidal ideation" to "active suicidal ideation with specific plan and intent" ([Posner et al 2011](#)). The C-SSRS Baseline version will be completed at screening (Visit 0), while the C-SSRS Since Last Visit version will be completed at the time points detailed in [Table 1](#). Patients with active suicidal ideation, as measured by a score of 4 or 5 on the C-SSRS at the screening visit, will not be eligible for the study.

In any event of suspected active suicidality (e.g. active suicidal ideation or intent, significant suicidal behavior) or clinical findings suggesting that the patient is dangerous to himself or herself, the patient should be referred for **immediate** psychiatric evaluation.

Patients with a positive C-SSRS suicidal ideation score of 1 and 2 will be monitored more closely and treated according to the investigator's medical judgment. Patients with C-SSRS or PBA-s suicidality scores 1 and 2 may be handled by study investigator/neurologist with a consultancy with psychiatrists where necessary per investigator's medical judgement.

Patients with C-SSRS or PBA-s suicidal ideation >2 (ie, 3, 4, 5), and all patients with C-SSRS suicidal acts, will be discontinued from treatment with study medication. A referral for psychiatric evaluation is required for AE/SAE of suicidal ideation/suicidal attempt or significant

² In accordance with the American Psychiatric Association's 2003 Practice Guideline for the Assessment and Treatment of Patients with Suicidal Behaviors.

increase in the suicidality scale from baseline (e.g., 2 point increase or higher) or C-SSRS or PBA-s suicidality score 3 and above.

Patients who are discontinued from treatment may continue their participation in the study and perform the scheduled visits and assessments, while off study drug. They will continue to be closely monitored by the investigator and will be referred for psychiatric evaluation per the investigator's medical judgment.

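### For an adverse event of suicidal ideation or attempt, protocol 7.1.6 takes the patient out of the study while 7.1.1 and related sections stop only the drug, and both tolerability endpoints count only patients who leave

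*Protocol*

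**What the plan says.** **The instruction to leave.** Protocol 7.1.6 covers expedited reporting of AEs of suicidal ideation or attempt. Once such an event is received, "the patient should be discontinued from the study and from study medication, and referred to a psychiatrist for evaluation and monitoring". It names study and medication separately and refers on to 7.1.7.

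**The instructions to stop the drug only.**
- Protocol 7.1.1, for the same event: "Patients with an AE/SAE of suicide ideation or attempt will be discontinued from treatment with study drug". It continues: "Patients who are discontinued from treatment may continue their participation in the study and perform the scheduled visits and assessments, while off study drug".
- Protocol 3.10.1 lists the event among its reasons for discontinuation without saying from what, then permits patients who stop drug for safety or tolerability to stay in the study.
- Protocol 7.8.1 covers suicidal ideation scores above 2 and suicidal acts. Patients stop study medication and "may continue their participation in the study and perform the scheduled visits and assessments, while off study drug".
- Protocol 7.1.7: "All patients for whom an adverse event of suicidal behavior/ideation was reported at any time during the study should be discontinued from study medication". It then asks discontinued patients to attend an early termination visit, and ends by saying that patients who stop medication for safety or tolerability "may continue in the study off drug and perform the scheduled visits and assessments".

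**A separate sentence on prohibited medication.** Protocol 7.1.7 also has a reason-coding exception for a milder AE that calls for a prohibited medication, "thereby requiring discontinuation of the patient". The reason recorded is then the medication and not the AE.

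**What is counted.** Protocol 2.3.1.2 and 9.8 and SAP 1.2.2 define two tolerability endpoints: the proportion who prematurely discontinue from the study, and the proportion who do so because of AEs. The AE summaries in protocol 9.7.2 and SAP 7.3 are likewise of AEs leading to withdrawal from the study. SAP 8 adds no further rule. SAP 5.2 summarizes withdrawals from treatment and from study, with reasons, as part of disposition.

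**The concern.** The protocol separates stopping drug from leaving the study elsewhere. In 3.10.1, slow-to-resolve hypokalemia ends study drug while the patient is asked to stay, whereas a confirmed QTcF above 500 msec ends study participation. So the wording of 7.1.6 cannot be read as a loose way of saying that the drug stops.

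Two sites that each follow the protocol could handle the same event differently, and the tolerability proportions would partly reflect which section each site applied. A patient who stops drug for this event and stays is absent, as a discontinuation, from both endpoints and from the tables of AEs leading to study withdrawal. That patient is visible only in the SAP 5.2 disposition summary, although the event itself still appears in the general AE tables.

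There is also a follow-up cost. A site that applies 7.1.6 ends the scheduled C-SSRS and PBA-s assessments for a patient whom 7.1.1 would let continue, and suicidality is a named safety endpoint.

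**Working it through.** The documents state no figure on this point, so there is none to reproduce. The check compares the text and then bounds the effect by arithmetic.

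**Step 1: classify one patient.** Take a patient with an AE of suicidal ideation who stops study drug that day.

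| Section followed | All-cause study discontinuation | Study discontinuation due to AE | SAP 5.2 treatment withdrawal |
|---|---|---|---|
| 7.1.6 | counted | counted | counted |
| 7.1.1, patient stays | not counted | not counted | counted |

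Only the last column is the same under both. Section 7.1.7 does not settle the matter. Its requirement concerns medication and its final sentence permits staying. Its early termination visit points the other way, because protocol 3.1 attaches early termination procedures to patients who withdraw from the study.

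**Step 2: size.** Inputs: N = 300 is the planned maximum in protocol 9.1, and N = 650 is that in SAP 2.4. The number of patients with the event, k, is assumed.

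Difference between the two readings = k/N for each endpoint. This is an upper bound for a given N, because staying is optional under 7.1.1.

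- One patient: 1/300 = 0.33 percentage points; 1/650 = 0.15.
- k = 3 (1% of 300): 3/300 = 1.0; 3/650 = 0.46.
- k = 9 (3% of 300): 9/300 = 3.0; 9/650 = 1.38.
- k = 15 (5% of 300): 15/300 = 5.0; 15/650 = 2.31.
- k = 0: no difference.

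Both values of N are ceilings, so a smaller enrolled number makes each patient weigh more.

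**Step 3: does correcting 7.1.6 settle the endpoint?** Let r be the share of patients who stop drug for any AE and s the share of those who stay off drug. If those who leave are recorded as leaving for the AE, the AE endpoint is r × (1 − s). With an assumed r of 5% it reads 5% at s = 0, 2.5% at s = 0.5 and 0% at s = 1. With r = 10% it reads 10%, 5% and 0%. A proportion based on stopping drug because of an AE would read r in every case. Making the sections agree removes the contradiction, but study discontinuation would still depend on how many patients choose to stay.

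**The case against.** The strongest reply is that this is one outlier sentence. Permission to continue off drug appears in the synopsis, 3.1, 3.10.1, 3.12.4, 6.1.5, 7.1.1, 7.1.7 and 7.8.1, and SAP 2.1 repeats it. These AEs must reach the sponsor within 24 hours, and the Medical Monitor must be told of every patient being considered for withdrawal because of an AE, so drift between sites would be limited. All of this stands, and it shows which rule the sponsor probably intends. It does not remove the contrary instruction.

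The consequences are also small. The analyses are descriptive, with no test or power at stake. SAP 5.2 retains the treatment-withdrawal data. Follow-up to resolution applies under 7.1.7 either way, and the early termination visit includes the C-SSRS and PBA-s. This too stands, and it limits the point to a minor one.

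Three stronger readings are tempting but unsupported.

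- *A second conflict over prohibited medication.* A reader might set "thereby requiring discontinuation of the patient" in 7.1.7 against 5.3, where the patient is "encouraged to continue in the study and complete the study visits in accordance with the study visit schedule". The 7.1.7 words sit in a rule for coding the reason for discontinuation and name neither study nor drug. The 5.3 sentence is conditioned on a randomized phase that this study does not have. Section 11.1.2 treats prohibited medication as a protocol violation and leaves the stay-or-leave decision to the sponsor. Opposite rules are not shown.
- *That 7.1.7 also removes patients with suicidal AEs from the study.* It is mixed: it requires stopping medication and ends by allowing continuation.
- *That suicidality follow-up is lost.* Under 7.1.6 the scheduled assessments end, but follow-up of the event does not.

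**Conclusion.** The contradiction between 7.1.6 and 7.1.1 is real and lies in the operative text. It reaches endpoints that belong to the primary objective, because the same patient counts in both tolerability proportions under one section and in neither, while staying, under the other. Each such patient moves each proportion by up to 0.33 points at N = 300. The total is unknown because the documents give no rates, and it could be zero.

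The point is minor. It affects the meaning of a descriptive proportion, and the information needed to interpret it is already tabulated in disposition. One limit should be kept in view: the SAP describes a later design than the protocol available here (up to 650 patients, re-entry, an internal safety committee). Whether the 7.1.6 sentence was still in force under that design cannot be told, so the finding rests on the protocol text itself.

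**What to change.** (a) In protocol 7.1.6, replace the instruction to leave the study with one rule: the patient stops study medication and is asked to continue scheduled visits off drug. In 7.1.7, limit the early termination visit to patients who actually leave the study.

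(b) In protocol 9.8 and SAP 8, report the proportion who permanently stopped study drug, overall and due to AEs, beside the two study-discontinuation proportions. Add AEs leading to drug discontinuation to the AE summaries in SAP 7.3. The treatment-withdrawal reasons already summarized under SAP 5.2 supply the data. Step 3 of the working shows why (a) alone is not enough.

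The cost is a few sentences and no new type of data. Some patients would be followed longer off drug. The drug-discontinuation proportion will usually be at least as high as the study-discontinuation proportion, which the report should explain.

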7.1.8. Overdose of Study Drug

Any dose of pridopidine, whether taken intentionally or unintentionally, in excess of that prescribed must be immediately reported to the sponsor.

7.1.9. Protocol Deviations Because of an Adverse Event

If a patient experiences an adverse event or medical emergency, departures from the protocol may be allowed on a case-by-case basis. After stabilization and/or treatment has been administered to ensure patient safety, the investigator or other physician in attendance must contact the individual identified in the Clinical Study Personnel Contact Information section of this protocol as soon as possible to discuss the situation. The investigator, in consultation with the sponsor, will decide whether the patient should continue to participate in the study.

7.2. Pregnancy

All pregnancies of women participating in the study and partners of men participating in the study that occur during the study, or within 14 days of completion of the study, are to be reported immediately to the individual identified in the clinical study personnel contact information section of this protocol, and the investigator must provide the LSO/CRO with the pregnancy form. The process for reporting a pregnancy is the same as that for reporting a SAE (see Section 7.1.5.3).

Any female patient becoming pregnant during the study will discontinue treatment. All patients (or partners) who become pregnant will be monitored for the outcome of the pregnancy (including spontaneous or voluntary termination). If the pregnancy continues to term, the outcome (health of the infant up to 8 weeks of age), including details of birth and presence or absence of any birth defect, congenital abnormalities, or maternal and newborn complications, will be reported to the sponsor. Any complication of pregnancy during the study and any complication of pregnancy that the investigator becomes aware of after termination from the study will be reported as an adverse event or SAE, as appropriate.

If the pregnancy does not continue to term, 1 of the following actions will be taken:

- For a spontaneous abortion, report as a SAE.
- For an elective abortion due to developmental anomalies, report as a SAE.
- For an elective abortion **not** due to developmental anomalies, report on the pregnancy form; do not report as an adverse event.

7.3. Clinical Laboratory Tests

All clinical laboratory test results outside of the reference range will be interpreted by the investigator as belonging to one of the following categories:

- abnormal but not a potentially clinically significant worsening from baseline
- abnormal and a potentially clinically significant worsening from baseline

A laboratory test result that has significantly worsened (according to medical judgment) from the baseline result will be recorded on the source documentation, transcribed onto the CRF as an adverse event, and monitored as described in Section 7.1.2. An adverse event includes a laboratory or diagnostic test abnormality (once confirmed by repeat testing) that results in the withdrawal of the patient from the study, the temporary or permanent cessation of treatment with study drug, or medical treatment or further diagnostic work-up.

In addition, potentially clinically significant values will be predefined by the sponsor for selected laboratory parameters (see Section 9.7.2) and will be detailed in the statistical analysis plan.

Clinical laboratory tests (serum chemistry, hematology, and urinalysis) will be performed at the time points detailed in Table 1. Clinical laboratory tests will be performed using the central laboratory. Specific laboratory tests to be performed are listed below.

7.3.1. Serum Chemistry

The following serum chemistry tests will be performed:

- calcium
- phosphorus
- sodium
- magnesium
- potassium
- chloride
- bicarbonate or carbon dioxide
- glucose
- blood urea nitrogen (BUN)
- creatinine
- cholesterol (low-density lipoprotein (LDL)/high-density lipoprotein (HDL)/total)
- uric acid

- alanine aminotransferase (ALT)
- aspartate aminotransferase (AST)
- lactic dehydrogenase (LDH)
- gamma-glutamyl transpeptidase (GGT)
- alkaline phosphatase (ALP)
- creatine phosphokinase (CPK) -in case of elevated creatine phosphokinase, the MB fraction should be measured
- total protein
- albumin
- total bilirubin
- direct bilirubin
- indirect bilirubin
- prolactin

7.3.2. Hematology

The following hematology tests will be performed:

- hemoglobin
- hematocrit
- red blood cell (RBC) count
- platelet count
- white blood cell (WBC) count and differential count
 - absolute neutrophil count
 - absolute lymphocyte count
 - absolute eosinophil count
 - absolute monocytes count
 - absolute basophil count
 - absolute atypical lymphocyte count

